**Actual Treatment Received in the Long Term Treatment Period:**

The actual treatment received in the long term treatment period is the IP the subject received from week 12 until EOS, regardless of treatment assigned by IRT. In cases where a subject received both efavaleukin alfa and placebo, the actual treatment received will be the efavaleukin alfa dose. In cases where a subject received multiple efavaleukin alfa doses, the actual treatment received will be based on the maximum of efavaleukin alfa doses received. **In cases where a subject received an efavaleukin alfa dose higher than the highest dose specified in the protocol, the actual treatment received will be the highest dose.**

**Actual Treatment Group in the Overall Study Period**

The actual treatment group in the overall study period is a combination of the actual treatment received in the induction period plus the actual treatment received in the long term treatment period (eg, placebo █ overall, AMG 592 █ ug █ overall, AMG 592 █ ug █ overall, AMG 592 █ ug █ overall, placebo █ induction/AMG 592 █ ug █ long term treatment).

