In the induction period, 4 dose groups are planned with a placebo group and 3 efavaleukin alfa dose groups: [REDACTED] µg [REDACTED] µg [REDACTED] and [REDACTED] µg [REDACTED]

In the long-term treatment period, subjects randomized to efavaleukin alfa during induction will remain on the same blinded dose throughout the long-term treatment period (both subjects who achieved clinical response at week 12 and those who did not achieve clinical response at week 12). Subjects randomized to placebo who achieved clinical response at week 12 will remain on placebo. Subjects randomized to placebo who did not achieve clinical response at week 12 will receive efavaleukin alfa [REDACTED] µg [REDACTED] in a blinded manner during the long-term treatment period.

For a full description of the investigational product doses, please refer to Section 6.1.1.

Statistical Considerations

The full analysis set will be used for analysis of the primary and secondary efficacy endpoints and will include all subjects randomized. The safety analysis set will include all randomized subjects who received at least 1 dose of investigational product.

Nominal p-values will be reported for the primary and secondary efficacy endpoints, with no adjustment for multiplicity.

The primary estimand will be analyzed using logistic regression to test the difference in clinical remission rates between efavaleukin alfa dose and placebo (Ge et al, 2011). The stratification factors as captured in the interactive response technology (IRT) will be included as covariates. The estimate of the risk difference between each efavaleukin alfa dose and placebo, the corresponding 2-sided 95% Wald confidence interval, and the p-value obtained from the logistic regression model will be provided. Missing primary endpoint data will be imputed using nonresponder imputation.

[REDACTED]

The primary analysis will occur when all subjects have had the opportunity to complete the week 12 visit. All primary and secondary objectives will be evaluated at the primary analysis.

For a full description of statistical analysis methods, please refer to Section 9.

[figure not shown]
Statistical Hypotheses

The primary hypothesis is that at least 1 efavaleukin alfa dose will have greater efficacy compared to placebo as measured by clinical remission rates at week 12 in subjects with moderately to severely active UC.

Sponsor Name: Amgen Inc.

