##### **First Dose Date:**

The first dose date is the date of administration of the first dose of IP; this may or may not be the same as randomization date.

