**Duration of Efavaleukin Alfa Exposure:**

The duration of efavaleukin alfa exposure will be derived as the date of the last administration of efavaleukin alfa plus 13 days (14 day window - 1), EOS, or data cutoff date, whichever occurs first, minus the date of first efavaleukin alfa administration + 1 day.

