**Treatment-emergent adverse event (TEAE):**

Treatment-emergent adverse events are events categorized as Adverse Events (AEs) starting on or after first dose of IP as determined by “Did event start before first dose of investigational product?” equal to “No” or missing on the Events eCRF and up to the EOS date.

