**Exposure-Adjusted Adverse Events:**

The exposure for the analysis of exposure adjusted TEAEs and serious TEAEs for the overall study period is defined for each subject as **(EOS – first dose date +1)**.

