#### **9.6 Safety Analyses**

##### **9.6.1 Adverse Events**

The Medical Dictionary for Regulatory Activities (MedDRA) version 27.0 or later will be used to code all events categorized as adverse events to a system organ class and a preferred term. The severity of each adverse event will be graded using CTCAE criteria version 5.0 or later ([Appendix A](#)). Summaries of adverse events during the induction adverse event exposure period will be presented by actual treatment received in the induction period. Exposure-adjusted subject incidence rates for the overall study period will be presented by actual treatment received in the overall study.

Subject incidence of all TEAEs, serious TEAEs, TEAEs leading to discontinuation from investigational product, fatal TEAEs, treatment-related TEAEs, treatment-related serious TEAEs, treatment-related TEAEs leading to discontinuation from investigational product,

treatment-related fatal TEAEs, and TEAEs of interest that occur in the induction adverse event exposure period will be summarized.

Subject incidence of treatment-emergent adverse events identified by COVID-19 standardized MedDRA queries and serious adverse events occurring on or after the COVID-19 infection that occur in the induction adverse event exposure period will also be summarized.

Subject incidence of events of interest (standardized MedDRA queries and/or Amgen Medical Queries) that occur in the induction adverse event exposure period will also be summarized according to their categories and preferred term. Events of interest could include but are not limited to Hypersensitivity, Tachyarrhythmias, Tachypnea, Hematopoietic Cytopenia, Drug Reaction with Eosinophilia, Leucocyte Changes, Infection and Infestation, Cytokine Release Syndrome, and Injection Site Reaction. Number of episodes and duration of treatment-emergent injection site reactions will be further summarized by treatment group.

In addition, summaries of TEAEs and serious TEAEs occurring in at least 5% of the subjects in any treatment arm and serious TEAEs occurring in at least 2% of the subjects in any treatment arm by preferred term that occur in the induction adverse event exposure period will be provided in descending order of frequency.

Summaries of TEAEs and serious TEAEs that occur in the induction adverse event exposure period will be tabulated by system organ class, preferred term, and grade. An overall summary of adverse events by toxicity grade will be provided.

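### The overall-period adverse event rate for subjects who switch from placebo to efavaleukin is not split at the switch, and the placebo column left behind is selected on week 12 response.

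*SAP*

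**What the plan says.** At week 12 the placebo arm divides. According to the Protocol synopsis, "Subjects randomized to placebo who achieved clinical response at week 12 will remain on placebo"; placebo nonresponders who continue are assigned to efavaleukin. For this purpose response is judged with the investigator's own endoscopy reading (Protocol 6.1.1.2). Subjects randomised to efavaleukin keep their dose whether or not they responded (Protocol Table 6-1).

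SAP 5.1 then sets the rules for overall-period safety:

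- **Group.** The overall-period treatment group "is a combination of the actual treatment received in the induction period plus the actual treatment received in the long term treatment period". The listed examples are placebo throughout, each efavaleukin dose throughout, and a separate sequence column in which placebo in induction is followed by efavaleukin ("induction/AMG 592").
- **Event window.** A treatment-emergent event is one whose eCRF answer on starting before the first dose of investigational product (IP) is no "or missing on the Events eCRF and up to the EOS date".
- **Denominator.** "The exposure for the analysis of exposure adjusted TEAEs and serious TEAEs for the overall study period is defined for each subject as" EOS minus first dose date plus one day.
- **Start of the clock.** "The first dose date is the date of administration of the first dose of IP", and IP includes placebo.

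SAP 9.6.1 puts these together: "Exposure-adjusted subject incidence rates for the overall study period will be presented by actual treatment received in the overall study". The measure is subject incidence, so a subject counts once per event type. Nothing in SAP 5.1 or 9.6.1 divides a switched subject's events or time at the first efavaleukin dose. A start date for that split does exist elsewhere in SAP 5.1: "The duration of efavaleukin alfa exposure will be derived as the date of the last administration of efavaleukin alfa", with an end rule, less the first efavaleukin date.

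**The concern.** Two things follow from these rules.

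First, the switch column combines roughly 12 weeks on placebo with the later weeks on drug. An event in the placebo weeks makes the subject a case in a column that carries the drug's name, and the same event type after the switch then adds nothing. A real drug effect is blurred.

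Second, the placebo-throughout column gives up the induction time and events of every nonresponder who switched. It keeps week 12 responders and, presumably, subjects who never entered the long-term period; the SAP does not say where the latter go. The continuous-efavaleukin columns keep responders and nonresponders alike. The reference column is therefore selected on a post-randomisation outcome and the drug columns are not. For any event that is more common when colitis is uncontrolled, a drug with no effect would look worse than placebo.

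These are the only overall-period adverse event rates planned, and readers will compare the columns. The induction tables cannot correct them, because their window closes by study day 90.

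**Working it through.** The plan states no adverse event rate, so there is no figure to reproduce. All rates, response shares and follow-up times below are assumptions for illustration. From the documents come the 12-week induction, up to 40 further weeks (12 + 40 = 52), and about 60 placebo subjects.

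**1. Placebo share of the switch column.** Share = 12 / EOS week.

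- EOS week 52: 12/52 = 23%
- EOS week 36: 12/36 = 33%
- EOS week 26: 12/26 = 46%

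SAP Section 11 records that the study was terminated for futility, so the shorter follow-up times are plausible.

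**2. Placebo time leaving the placebo column.** Time moved = nonresponders × 12/52 years. Assume all 60 complete week 12, all nonresponders switch, and follow-up runs to week 52. Total placebo time = (60 × 12 + responders × 40)/52.

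| Placebo response | Nonresponders | Time moved (years) | All placebo time (years) | Share moved |
|---|---|---|---|---|
| 20% | 48 | 11.1 | 23.1 | 48% |
| 30% | 42 | 9.7 | 27.7 | 35% |
| 45% | 33 | 7.6 | 34.6 | 22% |

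**3. Dilution in the switch column, using the SAP's estimator.** With constant hazards, exposure-adjusted subject incidence = [1 − exp(−cumulative hazard)] / (years to EOS). Assume 0.1 per year on placebo and 1.0 on drug.

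- As planned: cumulative hazard = (12 × 0.1 + (EOS − 12) × 1.0)/52.
- After a split: cumulative hazard = (EOS − 12)/52, divided by (EOS − 12)/52 years.

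| EOS week | As planned | After split |
|---|---|---|
| 52 | 0.547/1.000 = 0.55 | 0.537/0.769 = 0.70 |
| 36 | 0.384/0.692 = 0.55 | 0.370/0.462 = 0.80 |
| 26 | 0.253/0.500 = 0.51 | 0.236/0.269 = 0.88 |

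The split values still fall below 1.0 because the denominator does not stop at a subject's first event. That comes from the estimator, not the switch.

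**4. Selection with a null drug.** Assume 0.3 per year in responders and 0.9 in nonresponders whatever the treatment, with a placebo column of responders only. Responders are followed 52 weeks; nonresponders on efavaleukin are followed 52 or 30 weeks.

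- Placebo column: 1 − exp(−0.3) = 0.259.
- Nonresponder incidence: 1 − exp(−0.9) = 0.593 over 52 weeks; 1 − exp(−0.9 × 30/52) = 0.405 over 30 weeks.
- 50% nonresponse, 52 weeks: (0.5 × 0.259 + 0.5 × 0.593)/1 = 0.426; ratio 0.426/0.259 = 1.6.
- 50% nonresponse, 30 weeks: (0.130 + 0.203)/(0.5 + 0.288) = 0.421; ratio 1.6.
- 70% nonresponse, 52 weeks: 0.3 × 0.259 + 0.7 × 0.593 = 0.493; ratio 1.9.
- 70% nonresponse, 30 weeks: (0.078 + 0.283)/(0.3 + 0.404) = 0.513; ratio 2.0.

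**5. How far this depends on the assumptions.**

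- Six of 42 nonresponders never switch and stay in the placebo column to week 52: placebo = (18 × 0.259 + 6 × 0.593)/24 = 0.343, so the ratio is 0.493/0.343 = 1.4 instead of 1.9.
- Twofold contrast (0.6 against 0.3), 70% nonresponse, 52 weeks: (0.3 × 0.259 + 0.7 × 0.451)/0.259 = 1.5.
- Equal rates and equal follow-up: ratio 1.0, so no bias.

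**The case against.** A reader might infer that the SAP ignores the week 12 crossover, or that no long-term safety rate can be interpreted. The documents support neither. The overall-period definition itself creates a column for the switched subjects, so their data contaminate neither the continuous-efavaleukin columns nor the placebo-throughout column. The continuous-efavaleukin columns contain no placebo time, barring dosing errors. The switch column is a valid description of the whole sequence. The induction tables use induction treatment within the induction window, so all treated placebo subjects stay in placebo there.

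The context also limits the weight of the point. Safety is summarised descriptively. Long-term safety is an exploratory objective in Protocol Section 3, and the long-term objectives in SAP 2.1 now list only immunogenicity. The design itself removes a fair long-term placebo comparator, because no placebo nonresponder who continues is meant to stay on placebo. Tabulating by response status would not restore a randomised comparison and would make sparse cells. Finally, the assumed rates have no source in the documents, and the selection bias depends on them.

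All of this stands, and it sets the severity. It does not answer the narrower point: SAP 9.6.1 still plans overall-period rates, those for switched subjects mix two treatments, and the adjacent placebo column is conditioned on response.

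**Conclusion.** The concern holds in a limited form. The switch column is not an on-efavaleukin rate, with 23% to 46% of its time on placebo for EOS between week 52 and week 26. The placebo-throughout column is not a fair comparator for the efavaleukin columns.

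The mechanism follows from the SAP's definitions alone; its size does not. The dilution figures rest on an assumed tenfold drug effect. The spurious ratio of about 1.6 to 2.0 rests on an assumed threefold difference between nonresponders and responders, 50% to 70% nonresponse, and a placebo column of responders only. It is smaller with a weaker contrast, or if nonresponders who never entered the long-term period stay in that column.

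Severity is moderate: the randomised induction comparison is intact, but the overall-period rates would mislead as defined.

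**What to change.** Amend SAP 5.1 and 9.6.1 as follows.

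- Split each switched subject's events and time at the first efavaleukin dose. Time and events before it count to placebo; time and events from it go into a separate after-switch efavaleukin column.
- Take only the start date from the SAP's definition of efavaleukin exposure duration. That duration ends no later than 13 days after the last dose, whereas the event window runs to EOS, so the after-switch denominator should also run to EOS.
- Present placebo and efavaleukin rates separately for induction and for the period after week 12. Add a footnote that placebo time after week 12 comes mainly from responders and that the later comparison is not randomised.
- State which column holds subjects who never enter the long-term period.

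Tabulation by week 12 response status is optional and descriptive only; SAP 9.2 already does this for the disposition of placebo subjects.

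The cost is SAP wording, one more derived variable from dates already collected, and a few more table columns.

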**Duration of Induction Period IP Exposure:**

The duration of induction period IP exposure will be derived as the last date of IP administration prior to the week 12 endoscopy (or prior to EOS for subjects who do not have a week 12 endoscopy) plus 13 days (14 day window - 1), the day of first IP administration after the week 12 endoscopy - 1, EOS, or data cutoff date, whichever occurs first, minus the day of first IP administration + 1 day.

**Duration of IP Exposure (Overall Study):**

The duration of IP exposure (overall study) will be derived as the last date of IP administration prior to EOS plus 13 days (14 day window - 1), EOS, or data cutoff date, whichever occurs first, minus the day of first IP administration + 1 day.

**Duration of Efavaleukin Alfa Exposure:**

The duration of efavaleukin alfa exposure will be derived as the date of the last administration of efavaleukin alfa plus 13 days (14 day window - 1), EOS, or data cutoff date, whichever occurs first, minus the date of first efavaleukin alfa administration + 1 day.

**Duration of Long-term Treatment Period IP Exposure:**

The duration of long-term treatment period IP exposure for subjects who receive at least one dose of IP in the long-term treatment period will be derived as the last date of IP administration plus 13 days (14 day window - 1), EOS, or data cutoff date, whichever occurs first, minus the day of first IP administration after the [REDACTED] endoscopy +1 day.

**Completion of IP in the induction period:**

A subject will be considered as completing IP in the induction period if they do not discontinue IP prior to the **end of the induction period**. A subject will be considered as completing IP in the long-term treatment period if the End of IP reason is “Completed” on the End of IP eCRF.

**Treatment-emergent adverse event (TEAE):**

Treatment-emergent adverse events are events categorized as Adverse Events (AEs) starting on or after first dose of IP as determined by “Did event start before first dose of investigational product?” equal to “No” or missing on the Events eCRF and up to the EOS date.

**Treatment-related Adverse Event (TRAЕ):**

A treatment-related AE is any treatment-emergent AE with the relationship flag on the Events eCRF indicating there is a reasonable possibility that the event may have been caused by investigational medicinal product as determined by the investigator. In the unlikely event that the relationship is missing, the treatment-emergent event will be considered treatment-related and documented in a footnote of the treatment-related summary.

**Induction Adverse Event Exposure Period:**

Induction adverse event exposure period starts on the date of the first dose of IP up to min[EOS date, study day 90, max(week 12 IP date - 1, week 12 endoscopy date)].

**Exposure-Adjusted Adverse Events:**

The exposure for the analysis of exposure adjusted TEAEs and serious TEAEs for the overall study period is defined for each subject as **(EOS – first dose date +1)**.

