(including endoscopy) and mucosal biopsies for histopathology will be assessed at week 52/early termination visit.

If a subject discontinues investigational product prior to week 52, the subject will be encouraged to maintain the planned scheduled assessments through week 52. If the subject discontinues the study completely prior to week 52, the subject should complete an early termination (ET) visit (ie, week 52 visit procedures) which must be scheduled to allow for [REDACTED]

[REDACTED] who complete the week 52 endoscopy and who, in the opinion of the investigator, may benefit from continued treatment, will be assessed for eligibility to roll over into the Phase 2 Long Term Extension Study (20210210).

[REDACTED]

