### **9. Statistical Methods of Analysis**

#### **9.1 General Considerations**

All categorical variables will be summarized using the number and percent of subjects falling into each category and all continuous variables will be summarized using mean, standard deviation (SD), median, first quartile (Q1), third quartile (Q3), minimum, maximum, and number of subjects with observations.

Nominal p-values will be reported for the primary, secondary, and select exploratory efficacy endpoints, with no adjustment for multiplicity.

Safety endpoints will be summarized descriptively, including treatment-emergent adverse events and serious adverse events in the induction period, clinically significant changes in laboratory values and vital signs, and incidence of antidrug antibodies.

Exposure-adjusted treatment-emergent adverse events and serious adverse events will be summarized for the overall study period.

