Exposure-adjusted subject incidence rate of TEAEs, serious TEAEs, TEAEs leading to discontinuation from investigational product, fatal TEAEs, treatment-related TEAEs, treatment-related serious TEAEs, treatment-related TEAEs leading to discontinuation from investigational product, treatment-related fatal TEAEs, and TEAEs of interest will be presented for the overall study period.

Overall summary of subject incidence of TEAEs and by preferred term and worst severity grade will be provided by anti-AMG592 and Anti-IL-2 antibody status.

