### Appendix C. Handling of Dates, Incomplete Dates and Missing Dates

Imputation Rules for Partial or Missing Start Dates for Medical History, Procedures, AE, Conmeds (except corticosteroid recorded ended due to steroid tapering), Hospitalization dates.

Start Date		Stop Date						
		Complete: yyyymmdd		Partial: yyyymm		Partial: yyyy		Missing
		< 1 st dose	≥ 1 st dose	< 1 st dose yyyymm	≥ 1 st dose yyyymm	< 1 st dose yyyy	≥ 1 st dose yyyy	
Partial: yyyymm	= 1 st dose yyyymm	2	1	n/a	1	n/a	1	1
	≠ 1 st dose yyyymm		2	2	2	2	2	2
Partial: yyyy	= 1 st dose yyyy	3	1	3	1	n/a	1	1
	≠ 1 st dose yyyy		3		3	3	3	3
Missing		4	1	4	1	4	1	1

1=Impute the date of first dose; 2=Impute the first of the month; 3=Impute January 1 of the year; 4=Impute January 1 of the stop year

Note: For subjects who were never treated (first dose date is missing), partial start dates will be set to the first day of the partial month or first day of year if month is also missing.

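### The overall-period exposure-adjusted adverse event rate counts each subject once but divides by all follow-up to end of study, so common categories fall below the rate per time at risk

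*SAP*

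**What the plan says.** SAP Section 5.1, under Exposure-Adjusted Adverse Events, defines the denominator: "The exposure for the analysis of exposure adjusted TEAEs and serious TEAEs for the overall study period is defined for each subject as" EOS minus first dose date plus 1. The rule is the same for every subject, with or without an event.

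SAP Section 9.6.1 names the statistic: "Exposure-adjusted subject incidence rates for the overall study period will be presented by actual treatment received in the overall study". It then lists the categories: "Exposure-adjusted subject incidence rate of TEAEs, serious TEAEs, TEAEs leading to discontinuation from investigational product", followed by fatal events, the treatment-related versions and events of interest. Section 9.1 describes the same analysis without the word subject: "Exposure-adjusted treatment-emergent adverse events and serious adverse events will be summarized for the overall study period".

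The TEAE definition in Section 5.1 also runs to the end of study: "missing on the Events eCRF and up to the EOS date". That settles which events qualify. It does not say whether repeat events in one subject are counted.

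Neither document gives a numerator, formula or unit. Protocol Section 9.4.2.3.1 plans no exposure-adjusted analysis, so it does not fill the gap.

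**The concern.** A subject incidence numerator can rise by at most one per subject and category. After the first event that subject can add nothing more to the numerator, yet the stated denominator keeps adding time until EOS. The two parts suit different statistics. Full follow-up belongs with a count of all events; a count of subjects belongs with time up to the first event.

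The interpretation of the overall-period safety table is at stake. Most other adverse event incidence tables in Section 9.6.1 are tied to the induction exposure period, so these rates are the main description of adverse events over longer treatment. A reader would normally take an exposure-adjusted incidence rate as a rate per time at risk. For common categories the planned figure would be lower than that, by an amount that depends on how long subjects were followed. With the formula unwritten and the name differing between sections, two programmers could also produce different tables.

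**Working it through.** **Inputs from the documents.** The denominator is EOS minus first dose plus 1 (SAP 5.1). The numerator is subjects, counted once (SAP 9.6.1). Planned group size is 60 (Protocol 4.1.1). Longest follow-up after first dose: Protocol 4.4 allows 61 weeks in all, including a screening period of up to 35 days, so 61 − 5 = 56 weeks. The documents state no adverse event rate, so there is no planned figure to reproduce.

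**Assumptions.** Event shares p, the hazard pattern and event timing are assumed. A year is taken as 52 weeks unless stated.

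**Direction.** For each category, the sum of (EOS − first dose + 1) is at least the sum of (earlier of first onset and EOS − first dose + 1). The numerator is the same, so the planned rate can never exceed the rate per time at risk. This needs no assumption.

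**Size under constant hazard and common follow-up T.** Planned rate = p/T. Rate per time at risk = −ln(1−p)/T. Their ratio is p/(−ln(1−p)), which does not depend on T. With T = 56/52 years, per 100 subject-years:

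| Share with an event | Planned | Time at risk | Ratio |
|---|---|---|---|
| 5% | 4.6 | 4.8 | 0.975 |
| 10% | 9.3 | 9.8 | 0.949 |
| 20% | 18.6 | 20.7 | 0.896 |
| 50% | 46.4 | 64.4 | 0.721 |
| 70% | 65.0 | 111.8 | 0.581 |

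The shortfall is therefore about 5%, 28% and 42% at shares of 10%, 50% and 70%.

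**Timing.** Suppose 42 of 60 subjects have an event and all are followed for 56 weeks. The planned rate is 42/(60 × 56/52) = 65.0 per 100 subject-years, whenever the events occur. With every first event at week 4, time at risk is (18 × 56 + 42 × 4)/52 = 22.6 years, giving 185.7 (ratio 0.35). With every first event at week 28 it is (18 × 56 + 42 × 28)/52 = 42.0 years, giving 100.0 (ratio 0.65).

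**Dependence on follow-up.** With a constant hazard of 1 per year, the rate per time at risk is 100 per 100 subject-years at any length of follow-up. The planned rate, (1 − exp(−T))/T, is 86.1 at 16 weeks, 76.0 at 30 weeks and 61.2 at 56 weeks. With a hazard of 0.05 per year it is 5.0, 4.9 and 4.9, so rare categories hardly move.

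**Side effect of stopping at first onset.** SAP Appendix C sets many partial or missing onset dates to the first dose: "1=Impute the date of first dose". Such a subject contributes about one day at risk. In units of T, subjects with events contribute p/(−ln(1−p)) − (1−p). At p = 50% this is 0.721 − 0.500 = 0.221. If 5% of first onsets were imputed in this way, the time lost is 0.05 × 0.221 = 0.011, and the rate rises by a factor of 0.721/0.710, about 1.6%. The same steps give about 0.5% at p = 20% and 2.5% at p = 70%.

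**The case against.** The strongest reply is that the SAP never promises a rate per time at risk. It says exposure-adjusted and defines exposure for this very analysis. Subjects with an event over total follow-up is a coherent descriptive ratio, and its event window and exposure window both end at EOS. On that view only a one-line formula and label are missing. The point about coherence stands. But a label alone would leave a figure that is diluted for common categories and moves with follow-up, when a standard alternative is available from data already held.

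A second reply is that the constant-hazard benchmark flatters the alternative. That stands in part. If half the subjects have an event by week 12 and the hazard then drops to one fifth, the planned rate falls from 170.4 per 100 subject-years at 16 weeks to 65.2 at 56 weeks, a factor of 0.38. The rate per time at risk falls from 257.0 to 140.9, a factor of 0.55 (52.18 weeks to the year here). Stopping at first onset reduces the dependence on follow-up but does not remove it when events cluster early.

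A third reply is that imputed onset dates leave the planned denominator unchanged but affect the proposed one. That is correct, though small on the assumed 5%.

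A reader might also infer that the planned rates will hide or create differences between arms. Arithmetic for that exists: at equal follow-up, shares of 40% and 60% give a ratio of 0.60/0.40 = 1.50 as planned and ln(0.40)/ln(0.60) = 1.79 per time at risk. The documents do not support it as a finding. No ratio or test of overall-period adverse event rates is planned. The columns are not purely randomized groups: the overall group "is a combination of the actual treatment received in the induction period plus the actual treatment received in the long term treatment period", and continuing placebo nonresponders move to efavaleukin alfa at week 12. Nor is any imbalance in follow-up known. Exposure runs to EOS rather than to last dose, and for subjects who stop treatment early "the subject will be encouraged to maintain the planned scheduled assessments through week 52". The study was also terminated for futility after the third interim analysis (SAP Section 11), which limits what rests on this table.

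**Conclusion.** The mismatch is real and worth correcting. As written, SAP Sections 5.1 and 9.6.1 together give subjects with an event per total follow-up time. For common categories this understates the rate per time at risk and depends on length of follow-up.

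The direction is certain. The size rests on assumed event shares, constant hazard and common follow-up: about 5% low at a 10% share, 28% at 50% and 42% at 70%, and more if events come early. Rare categories, the induction-period adverse event tables and the efficacy analyses are not materially affected. The analysis is descriptive, with no planned between-group test, so no error rate or power is involved.

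It might also be inferred that the placebo-to-efavaleukin column has to be split at the switch. That does not follow: the column is already separate and labelled, and a split could place onsets imputed to first dose in the placebo part.

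**What to change.** In SAP Section 5.1, write the formula: subjects with at least 1 event in the category, divided by the sum over subjects of time from first dose to the earlier of first onset in that category and EOS, with the unit stated. If full follow-up to EOS is preferred, count all events and call the result an event rate. Use one name for the statistic in Sections 9.1 and 9.6.1.

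Under the first option, footnote the number of adverse events whose onset was imputed to first dose, because these shorten time at risk and raise the rate slightly.

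The cost is SAP wording and reprogramming of one table family, with person-time calculated separately for each category from data already held. Data collection and the induction tables do not change.
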